	No Response	Response
No Toxicity	77	16
Toxicity	26	5

A flat Dirichlet prior distribution for experimental Panitumumab was chosen reflective of information from the equivalent of 4 patients with the same marginal distributions as for Panitumumab (e.g., RR rate of 17% and toxicity rate of 25%).

This regimen of Panitumumab will be considered worthy of further investigation if it elicits an increase in RR to 25% with acceptable toxicity. A 25% toxicity rate is considered unacceptable. Thus, interim monitoring rules, assuming the prior distributions above, were constructed that meet the following two conditions,

- 1) $\Pr(\emptyset_S, \text{Toxicity} < \emptyset_E, \text{Toxicity} \mid \text{data}) > 0.95$ and,
- 2) $\Pr(\emptyset_S, \text{Response} < \emptyset_E, \text{Response} \mid \text{data}) < 0.05$

Where $\emptyset_{E, \text{Toxicity}}$ and $\emptyset_{E, \text{Response}}$ are the true toxicity and response rates for Panitumumab, respectively. The first rule provides for stopping the study if excessive toxicity is highly probable (i.e., probability $> 95\%$) for Panitumumab. The second condition will stop the study early if the data suggest that it is unlikely (i.e., probability $< 5\%$) that response rate

of the drug is 17%. Assuming the minimum number of patients is 1, the maximum number of patients is 17 and the cohort size is 1.

The monitoring rule for the toxicity rate, based on these assumptions and monitoring conditions above is found in the following table. For example, accrual will cease if 4 or more patients experience toxicities among the first 5 patients treated or if 6 or more patients experience toxicities among the first 10 patients.

Stop accrual if the number of toxicities is equal to or greater than indicated (i.e., # toxicities) among the number of patients evaluated (i.e., # patients)						
# Toxicities	3-4	4-6	5-9	6-11	17-14	8-16
# Patients	3-4	5-6	7-9	10-11	12-14	15-16

Monitoring the response rate, based on the above assumptions and monitoring will begin after 1 patient is treated (on an intent-to-treat basis). Following this rule, the trial will be terminated if $[\# \text{ Response}] / [\# \text{ patients evaluated}] \leq 0/8$. For example, accrual will cease if 0 or fewer patients experience a response in the first 8 patients treated.

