Multc Lean Desktop (version 2.0.0) was used to generate the toxicity and futility stopping boundaries and the OC table. In order to utilize the software for the design, a beta (21, 103) prior was assumed for the historical control response rate and a beta (31, 93) prior was assumed for the historical control toxicity rate.

The probability of stopping the study early if the true response rate of the Panitumumab was not better than 17% was 35%. Probabilities of stopping early for high true toxicity rates (i.e., 37%) were 57% when the true RR rate was 17% and 48% when true RR was 25%.

Operating characteristics for simultaneous monitoring response and toxicity rates for patients treated with Panitumumab.				
True RR	True Toxicity Rate	True Probability Vector (RR/TX, RR/NTX, NRR/TX, NRR/NTX)	Probability of Stopping	Average number of patients treated
8%	12%	(0.010,0.070,0.110,0.810)	0.5174	12
8%	25%	(0.020,0.060,0.230,0.690)	0.5637	12
8%	37%	(0.030,0.050,0.340,0.580)	0.6885	10
17%	12%	(0.020,0.150,0.099,0.730)	0.2319	15
17%	25%	(0.042,0.127,0.207,0.622)	0.3055	14
17%	37%	(0.062,0.107,0.307,0.523)	0.5042	12
25%	12%	(0.030,0.220,0.090,0.660)	0.1078	16
25%	25%	(0.062,0.187,0.187,0.562)	0.1934	15
25%	37%	(0.092,0.157,0.277,0.472)	0.4241	13

Where Will Participants Be Enrolled:

Only at MDACC

Is this an NCI-Cancer Therapy Evaluation Protocol (CTEP)? No

Is this an NCI-Division of Cancer Prevention Protocol (DCP)? No

Estimated Accrual:

Total Accrual at MDACC: 27

Estimated monthly accrual at MDACC: 1-2

Accrual Comments:

The total accrual for this study is 27. There are 10 patients already enrolled and 3 have been treated with combination therapy, and 17 patients are to be enrolled for the single agent treatment.

Do you expect your target population to include non-english speaking participants? No

Location of Treatment:

This protocol is performed on an Outpatient basis.

Length of Stay: What is the length & frequency of hospitalization?

NA

Return Visits: How often must participants come to MDACC?

Every 2 weeks

Home Care: Specify what, if any, treatment may be given at home.

NA

Name of Person at MDACC Responsible for Data Management: [[name]](#)

Prior protocol at M. D. Anderson:

Has the Principal Investigator ever had a clinical or behavioral protocol at MDACC that accrued patients?
Yes

Data Monitoring Committee:

Is treatment assignment randomized? No

Is this a blinded or double-blinded study? No

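### The text overstates the probability of early stopping at 37% toxicity: 57% and 48%, against 50.4% and 42.4% in the table directly below it

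*Combined protocol and SAP*

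**What the plan says.** All of this is in the combined protocol and SAP, Statistical Considerations, Sample Size and Endpoint Monitoring.

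- **Text on high toxicity.** The early-stopping probabilities are summarised as "i.e., 37%) were 57% when the true RR rate was 17% and 48% when true RR was 25" (per cent).
- **Sentence before it.** "The probability of stopping the study early if the true response rate of the Panitumumab was not better than 17% was 35" (per cent). No toxicity rate is named.
- **Operating characteristics table, directly below.** At 37% toxicity the probability of stopping is 0.5042 for a response rate (RR) of 17% and 0.4241 for RR 25%. The other two RR 17% rows are 0.2319 (toxicity 12%) and 0.3055 (toxicity 25%).
- **Futility rule.** "accrual will cease if 0 or fewer patients experience a response in the first 8 patients treated".
- **Toxicity rule.** A table of cut-offs with worked examples, one of which is "accrual will cease if 4 or more patients experience toxicities among the first 5 patients treated".
- **Looks.** "the maximum number of patients is 17 and the cohort size is 1".
- **Prior for the experimental regimen.** It is called flat and also described as "reflective of information from the equivalent of 4 patients with the same marginal distributions as for Panitumumab", with a response rate of 17% and a toxicity rate of 25%. The historical controls are beta(21, 103) for response and beta(31, 93) for toxicity.

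The boundaries and the table are attributed to the same software. No second design or alternative definition of stopping is given.

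**The concern.** The text and the table describe the same scenarios, identified by the same response and toxicity rates, and they differ by far more than rounding. Both cannot describe one design.

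These sentences are the plan's prose summary of how well monitoring would halt a regimen that is too toxic. A reader who relies on them takes the chance of not stopping early at 37% toxicity to be 43% (RR 17%) and 52% (RR 25%). The table implies 50% and 58%. The text therefore errs in the reassuring direction.

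**Working it through.** **1. Text against table at 37% toxicity**

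| Scenario | Text | Table | Difference |
|---|---|---|---|
| RR 17% | 57% | 50.42% | 57 − 50.42 = 6.58 points |
| RR 25% | 48% | 42.41% | 48 − 42.41 = 5.59 points |

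**2. Which side follows from the printed rules?**

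Inputs, all from the section cited:
- Maximum of 17 patients, cohort size 1, looks after patients 1 to 16 (the printed toxicity table ends at 16).
- Futility: stop if there are 0 responses at any look from n = 8.
- Toxicity: stop at 3 or more for n = 3–4, 4 for 5–6, 5 for 7–9, 6 for 10–11, 7 for 12–14, 8 for 15–16. The row of toxicity counts is garbled in the available text. The worked examples fix the cut-offs 4 and 6; the rest are read as the sequence 3 to 8.
- Response and toxicity independent at the table's marginal rates.

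Method: an exact recursion on the pair (responses R, toxicities T). At each n, the probability of each state (R, T) that has not stopped is split over the four outcomes, with probabilities rt, r(1−t), (1−r)t and (1−r)(1−t). Mass that reaches a boundary is added to the stopping probability and removed.

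| RR | Toxicity | Table | Recomputed |
|---|---|---|---|
| 8% | 12% | 0.5174 | 0.5174 |
| 8% | 25% | 0.5637 | 0.5637 |
| 8% | 37% | 0.6885 | 0.6885 |
| 17% | 12% | 0.2319 | 0.2319 |
| 17% | 25% | 0.3055 | 0.3055 |
| 17% | 37% | 0.5042 | 0.5042 |
| 25% | 12% | 0.1078 | 0.1078 |
| 25% | 25% | 0.1934 | 0.1934 |
| 25% | 37% | 0.4241 | 0.4241 |

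All nine agree to four decimals, which also supports the reading of the garbled row. The average numbers treated agree too after rounding (for example 12.1 and 12.9 against 12 and 13 in the two rows at issue). The printed probability vectors, "0.062,0.107,0.307,0.523" and "0.092,0.157,0.277,0.472", sum to 0.999 and 0.998. Rescaled to sum to 1, they give 0.5038 and 0.4238, so rounding of the vectors explains nothing.

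**3. Can another reading produce the text's figures?**

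| Variant | RR 17%, tox 25% | RR 17%, tox 37% | RR 25%, tox 37% |
|---|---|---|---|
| Text | 35% (toxicity rate not named) | 57% | 48% |
| Printed rules | 30.6% | 50.4% | 42.4% |
| Added look at n = 17 (assumed cut-off 8; not printed) | 31.0% | 52.7% | 45.1% |
| Futility from n = 7, with that added look | 35.1% | 55.6% | 47.1% |
| Futility from n = 6 | 39.7% | 56.9% | 47.4% |
| Toxicity rule alone | – | 36.0% | 36.0% |

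No variant gives 35%, 57% and 48% together, and the two nearest do not use the printed 0/8 rule.

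**4. What kind of stopping is counted?**

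Text and table both count a stop for toxicity or futility. Under the printed rules at 37% toxicity, the toxicity boundary is met in 32.8% of trials (RR 17%) and 34.6% (RR 25%). The remaining 17.6% and 7.8% stop for futility alone: 32.8 + 17.6 = 50.4 and 34.6 + 7.8 = 42.4.

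**5. Does the stated prior explain the text?**

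Four patients' worth of information at 17% and 25% gives beta(4 × 0.17, 4 × 0.83) = beta(0.68, 3.32) for response and beta(1, 3) for toxicity. Against the historical beta(21, 103), the probability that the experimental response rate is the higher is 0.075 at 0/8, 0.052 at 0/10 and 0.043 at 0/11. Futility at the 0.05 limit would thus begin at 0/11, not 0/8. The toxicity cut-offs would become 4 at n = 4, 5 at n = 6, 6 at n = 9 and 8 at n = 14, with the others up to n = 16 unchanged. The stopping probabilities would be 18.8%, 38.7% and 32.6%, and the gaps to the text 35 − 18.8 = 16.2, 57 − 38.7 = 18.3 and 48 − 32.6 = 15.4 points. A two-patient prior, by contrast, gives 0.041 at 0/8 (0.051 at 0/7), every printed cut-off, and hence the table.

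**The case against.** The strongest reply is that the correct figures are printed immediately below the sentence, the operative boundaries are unaffected, and the study closed to new patient entry on 04/26/2016. That stands, and it limits the consequence to an accurate record and accurate reporting of the design.

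Four narrower points also deserve weight.

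- **Toxicity protection.** Both sets of figures are stops for any reason. Replacing 57% and 48% with 50% and 42% without saying so would still overstate protection from toxicity. This stands, and the correction should say it.
- **The prior.** Whether the boundaries follow from the stated prior is a separate question from text against table, and the larger gaps of 15 to 18 points compare the text with a design that is not printed. That is fair; the error claimed here is 5.6 to 6.6 points. The plan also calls the prior flat while giving it 17% and 25% marginals. A literally flat Dirichlet(1,1,1,1) would give 26.0%, 58.2% and 58.2%, so not every reading of the prior moves away from the text. That reading contradicts the stated marginals, however, and does not give the three text figures either.
- **The 35%.** With no toxicity rate named, it has no definite counterpart in the table. It can be called unmatched. An error of 4.5 points (35 − 30.55) follows only if 25% toxicity was meant.
- **Cost.** Re-deriving the boundaries would change operative stopping rules, which is more than a rerun of software. This stands.

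None of these removes the contradiction.

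**Conclusion.** The concern holds. At 37% toxicity the text overstates the probability of early stopping by 6.6 points (RR 17%) and 5.6 points (RR 25%) relative to the table. The table follows exactly from the printed boundaries and the text does not. The 35% in the preceding sentence matches no RR 17% row.

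The contradiction itself needs no assumption. The finding that the text is the wrong side rests on looks after patients 1 to 16, independence of response and toxicity, and the garbled cut-off row read as 3, 4, 5, 6, 7, 8; the nine-row match supports all three. The mismatch between the four-patient prior and the printed boundaries further assumes that this prior has the stated 17% and 25% marginals.

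This should be corrected, but by itself it does not affect the sample size or the printed stopping rules.

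**What to change.** 1. First reconcile the printed boundaries with the stated four-patient prior, and state which is operative. That choice is the sponsor's.
2. If the printed boundaries stand, correct the description of the prior. In the text, replace 57% and 48% with 50% and 42%, and say that these are probabilities of stopping for any reason. It would help to add that the toxicity boundary itself is met in about 33% and 35% of trials.
3. Replace 35% with the table value for a named toxicity rate: 23% at 12% toxicity, 31% at 25%, or 50% at 37%.
4. If the boundaries are re-derived from the stated prior, recompute both the text and the table.

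Under steps 2 and 3 the cost is a wording correction, and the stated figures become less favourable at 37% toxicity. Step 4 needs a rerun of the design software and would alter the operative futility and toxicity boundaries, so it would be a design amendment and not an editorial change.
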